#### **8.4 Withdrawal of individual subjects**

Subjects can leave the study at any time for any reason if they wish to do so without any consequences. Patients will then receive regular care. The investigator can decide to withdraw a subject from the study for urgent medical reasons.

##### **8.4.1 Specific criteria for withdrawal (if applicable)**

Not applicable

#### **8.5 Replacement of individual subjects after withdrawal**

Not applicable for the trial.

**For the GODIVA-bone substudy:** In case patients withdraw after informed consent for the substudy before the first pre-treatment data gathering, the subject is replaced ensuring the 200 patients baseline data-sets. As the change over two years is exploratory, subjects from which follow-up (at 2 years) data are missing are not replaced.

#### **8.6 Follow-up of subjects withdrawn from treatment**

As KP and KJD are interventions during a (reasonably) short period we do not expect withdrawal from treatment. In the unlikely event a patient does not undergo the treatment he/she was randomized to, he/she will remain followed according to the protocol. Note that this can be only one way, refusing KP will not result in KJD as this is not approved reimbursed standard of care. Reasons for deviations from the treatment protocol will be recorded and the patients will be accounted for in the analysis appropriately (ITT and in PP these patients will be excluded).

### **8.7 Premature termination of the study**

We do not expect premature termination of the study to be necessary, as both treatments have been used (extensively) previously in studies and clinical practice and our study follows clinical practice.

The additional image and sample acquisition for the GODIVA-bone substudy is relatively simple and with that feasible and is not considered a reason for premature termination.

## 9. SAFETY REPORTING

### 9.1 Temporary halt for reasons of subject safety

In accordance to section 10, subsection 4, of the WMO, the sponsor will suspend the study if there is sufficient ground that continuation of the study will jeopardise subject health or safety. The sponsor will notify the accredited METC without undue delay of a temporary halt including the reason for such an action. The study will be suspended pending a further positive decision by the accredited METC. The investigator will take care that all subjects are kept informed.

### 9.2 AEs, SAEs and SUSARs

#### 9.2.1 Adverse events (AEs)

Adverse events (AE) are defined as any undesirable experience occurring to a subject during the study, whether or not considered related to KJD or KP. All adverse events reported spontaneously by the subject or observed by the investigator, or his staff will be recorded.

#### 9.2.2 Serious adverse events (SAEs)

A serious adverse event is any untoward medical occurrence or effect that

- results in death;
- is life threatening (at the time of the event);
- requires hospitalisation or prolongation of existing inpatients' hospitalisation;
- results in persistent or significant disability or incapacity;
- is a congenital anomaly or birth defect; or
- any other important medical event that did not result in any of the outcomes listed above due to medical or surgical intervention but could have been based upon appropriate judgement by the investigator.

An elective hospital admission will not be considered as a serious adverse event.

The investigator will report all SAEs to the sponsor without undue delay after obtaining knowledge of the events.

The sponsor (UMCU) will report the SAEs through the web portal *ToetsingOnline* to the accredited METC that approved the protocol, within 7 days of first knowledge

for SAEs that result in death or are life threatening followed by a period of maximum of 8 days to complete the initial preliminary report. All other SAEs will be reported within a period of maximum 15 days after the sponsor has first knowledge of the serious adverse events.

Exceptions to above SAE reporting to the accredited METC are the following expected, pre-determined SAEs (although these of course will be documented):

- o a KP or revision surgery of the index knee within 2 years after (failure of) the KJD/KP treatment
- o With respect to KJD, a pin tract infection for which the patient is treated temporarily with intravenous antibiotics

These SAEs will be reported in line listings, in annual progress reports.p

### **9.2.3 Suspected unexpected serious adverse reactions (SUSARs)**

Not applicable.

## **9.3 Annual safety report**

Not applicable

## **9.4 Follow-up of adverse events**

All AE and SAE will be monitored and treated according to standard of care and will be followed until they have abated, or until a stable situation has been reached. Depending on the event, follow up may require additional tests or medical procedures as indicated, and/or referral to the general physician or a medical specialist.

SAEs need to be reported till end of study, as defined in the protocol

## **9.5 Data Safety Monitoring Board (DSMB) / Safety Committee**

Not applicable

## 10. STATISTICAL ANALYSIS

### 10.1 Primary study parameter(s)

Given the obvious advantages of preserving a patients' own knee, KJD needs to demonstrate 'non-inferiority' on the medium-long (2 year) term.

A full statistical analysis plan (SAP) will be in place prior to the analysis of trial data. All analyses and patient populations will be predefined in this SAP. Both intention-to-treat (ITT) and per protocol (PP) analyses have biases so neither can be regarded the 'gold standard' for non-inferiority trials but these approaches can make critical differences to the results of a trial (18). The trial will be analyzed and reported according to CONSORT extension for Non-Inferiority and Equivalence Randomized Trials (19).

The primary endpoint, the total WOMAC score at 2 years, will be compared between groups using (multivariable) random effects (mixed) modelling to account for the nested and longitudinal structure of the data over the 24 months follow-up. In case residuals of the model are not normally distributed, transformed scores will be used in the regression modelling. In this analysis time will be used as a categorical variable (5, 8, 12 and 24 months), and an interaction between time and the treatment-arm variable will also be included. A random intercept at patient level as well as at center level will be included. The stratification factors for randomization, center (using a random intercept) and gender, as well as a limited number of a priori defined prognostic factors (i.e. baseline WOMAC total score, age, BMI, and severity of cartilage damage) will be accounted for in this analysis used as fixed covariates. Baseline WOMAC score will be used as a continuous covariate (similar to the outcome variable), as well as age and severity of cartilage damage which can be regarded a reasonable assumption given the limited, expected range (in patients with age  $\leq 65$  and severe knee OA (K&L grade  $> 2$ )). As we expect that the effect of BMI may be non-linear, we will use BMI as a categorical variable using the CDC classification (BMI  $< 18.5$ , underweight;  $18.5$  to  $<25$ , healthy weight; BMI  $25.0$  to  $<30$ , overweight; BMI  $30.0$  to  $< 35$  (max allowed in the study) obesity).

A random effect of time will also be tested in the model. The difference in mean total WOMAC score at 24 months between treatment groups will be estimated from this model with a 95% confidence interval (CI). The lower limit of this interval will be compared to the non-inferiority limit. If the lower limit of the confidence interval does not overlap the non-inferiority limit, KJD will be considered non-inferior. The non-inferiority limit is predefined

and accepted as 15 for the primary outcome (WOMAC total score) (See also at sample size calculation, 14).

The above analysis will be performed primarily on the per protocol (PP) population, i.e. patients that received their randomised treatment (and completed the 6 week distraction period for patients randomised to KJD only). The analysis will be repeated, for sensitivity reasons, for the ITT population defined as all patients who were randomized to one of the treatments.

A secondary analysis of the primary endpoint will be performed using (simple, multivariable) linear regression modelling, using only the 24 month WOMAC total scores. Multiple imputation will be used with > 10% missing data. This analysis will also be made the primary analysis when assumptions for the mixed model analysis do not seem to hold or convergence problems occur.

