#### 4.4 Sample size calculation

In the recently performed 'StWP' evaluation of KJD by 'Zorg Instituut Nederland (ZiN)' a non-inferiority limit for the 'crucial' endpoint of total WOMAC score at 2 years (the primary endpoint here) was defined at 15.

Assuming a 'true' difference in total WOMAC score of 12 points in favor of KP based on previous (pilot) data with an SD of 15 (14), 527 patients need to be recruited into each arm to obtain 90% power (2.5% one-sided significance) to demonstrate 'non-inferiority' (calculated using the power procedure in SAS 9.4). To account for missing data and loss to follow-up, we increase the sample size with ~15% and will include 600 patients per group.

**Sample size considerations for the GODIVA-bone substudy:** The response outcomes to use for the prediction models have an occurrence between ~30% and ~50%, indicating that with the 200 patients included (2/3 responder, i.e. 134 patients) we will have between 60 and 100 events for our analysis (between 40 and 67 for model development). Based on general rule of thumb, where at least 5-10 events per variable studies are needed we will have room for maximally 13 predictive parameters. To adhere to this, when needed, we will use data reduction techniques (e.g. principal component analysis or other feature reduction/selection techniques) or analysis techniques, suitable for sparse data, like penalized regression techniques to be defined in the SAP. For the secondary aim (explorative) we will relate changes in bone parameters to changes in pain (WOMAC pain) and cartilage tissue repair (radiographic joint space width increase) over a period of two years. The same parameters as explored in the predictive analysis as well as changes therein will be used as independent variables in this analysis.

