**7.6 Dosages, dosage modifications and method of administration**

**7.7 Preparation and labelling of Non Investigational Medicinal Product**

**7.8 Drug accountability**

## 8. METHODS

### 8.1 Study parameters/endpoints

#### 8.1.1 Main study parameter/endpoint

The primary outcome of this randomized non-inferiority trial is the WOMAC total score at 2 years. The Western Ontario and McMaster Universities Arthritis Index (WOMAC) total score (0-100; higher is better) is a combination of (sub scores for) pain, disabilities, and stiffness, all relevant to the patient, making it the preferred primary outcome for our study.

The WOMAC score is calculated based on the KOOS questionnaire (Appendix A), which is a freely available questionnaire (unlike the WOMAC questionnaire) and contains the same questions as the WOMAC and questions for two additional domains function in daily living and function in sports and recreation. Therefore, WOMAC scores are often calculated based on this instrument. Contrary to the KOOS scores, a total score (based on the individual sub-scores) can be calculated for the WOMAC, which is not advised for the KOOS (see [www.koos.nu](http://www.koos.nu)).

Finally, the WOMAC total score is one of the 'crucial endpoints' as defined in the StWP process by ZiN to decide on reimbursement for this promising treatment in consultation with all stakeholders (such as the professional and patient associations).

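### If residuals are non-normal, section 10.1 moves the primary model to transformed WOMAC scores, but the non-inferiority limit stays at 15 raw points

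*Protocol*

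**What the plan says.** Section 10.1 specifies a mixed model for WOMAC total score over 5, 8, 12 and 24 months, and adds: "In case residuals of the model are not normally distributed, transformed scores will be used in the regression modelling". It names no transformation.

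The decision follows from the same model: "The difference in mean total WOMAC score at 24 months between treatment groups will be estimated from this model", with a 95% confidence interval. "The lower limit of this interval will be compared to the non-inferiority limit", and that limit is described as predefined "and accepted as 15 for the primary outcome (WOMAC total score)".

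The units are fixed elsewhere. Section 8.1.1 defines the endpoint: "The Western Ontario and McMaster Universities Arthritis Index (WOMAC) total score (0-100; higher is better)". Section 4.4 gives the margin for the "endpoint of total WOMAC score at 2 years (the primary endpoint here) was defined at 15" and bases the sample size on a "difference in total WOMAC score of 12 points in favor of KP based on previous (pilot) data with an SD of 15".

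Section 10.1 also names a linear regression on the 24-month scores only, and says: "This analysis will also be made the primary analysis when assumptions for the mixed model analysis do not seem to hold or convergence problems occur". Section 10.2 applies the primary strategy to continuous secondary outcomes. Section 2 sets a non-inferiority aim for the secondary patient-reported outcomes.

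**The concern.** Two fixed instructions in section 10.1 do not fit together. One changes the scale of the outcome when a residual check fails. The other compares the result with a limit that has meaning only on the original scale. Nothing in the protocol converts the limit, prescribes a route back to raw points, or says that the test stays on the raw scale.

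There is a second overlap. Normal residuals are themselves a mixed-model assumption, so one failed check could lead to a transformed mixed model or to a different primary analysis. The two can be read as competing responses or as successive steps. The text does not say which, and it does not exempt the fallback regression from transformation.

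With only 3 points between the assumed difference and the margin, a shift of 1 to 2 points in the estimate uses up much of the room that the sample size relies on. The choice of scale would also be made after looking at outcome data in an open trial.

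**Working it through.** **1. The plan's own figure.** Inputs from section 4.4: margin 15, true difference 12, SD 15, one-sided 2.5%, power 90%.

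n per arm = 2 × SD² × (1.960 + 1.282)² / (15 − 12)² = 2 × 225 × 10.51 / 9 ≈ 526. The noncentral-t version gives 527 (power 0.9004), the protocol's figure.

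Check at 527: SE = 15 × √(2/527) = 0.924, and power = Φ(3/0.924 − 1.96) = 0.901. Margin, difference and SD are therefore all raw WOMAC points.

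**2. Assumptions for the illustration.** The protocol gives no KP mean and no transformation. Assumed here:
- deficit = 100 − WOMAC, gamma distributed
- square-root transform of the deficit
- mean KP deficit 12, 15, 20 or 25
- SD 12 or 15 in each arm
- 527 per arm

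For a gamma deficit with mean m and SD s: k = (m/s)², θ = s²/m, E[√deficit] = √θ × Γ(k + 0.5)/Γ(k).

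**3. One case in full.** KP deficit 15, KJD deficit 30 (a true loss of exactly 15), SD 15 in both arms.
- KP: k = 1, θ = 15, mean root = √15 × Γ(1.5)/Γ(1) = 3.432, squared 11.78.
- KJD: k = 4, θ = 7.5, mean root = √7.5 × Γ(4.5)/Γ(4) = 5.309, squared 28.19.
- Difference on the root scale: 1.88.
- Difference after squaring the mean roots: 28.19 − 11.78 = 16.41 points, where the truth is 15.

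The excess arises because squaring a mean root drops the root-scale variance, which differs by arm: 15 − 11.78 = 3.22 in KP and 30 − 28.19 = 1.81 in KJD. The gap is 1.41. Adding one common residual variance to both means cancels in the difference and changes nothing.

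**4. All 16 scenarios.** Back-transformed reading of a true 15-point loss, in points:

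| SD KP / KJD | KP deficit 12 | 15 | 20 | 25 |
|---|---|---|---|---|
| 12 / 12 | 16.28 | 16.01 | 15.70 | 15.51 |
| 12 / 15 | 15.58 | 15.37 | 15.14 | 15.02 |
| 15 / 12 | 17.36 | 17.04 | 16.58 | 16.25 |
| 15 / 15 | 16.66 | 16.41 | 16.03 | 15.76 |

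On the root scale itself, the same 15-point loss ranges from 1.36 to 2.18 units. No single converted margin exists.

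**5. Effect on the decision.** Simulation with 20,000 replicates. Non-inferiority is declared if the upper 95% limit of the loss is below 15, with a delta-method SE for the back-transformed difference. SD 15 in both arms:

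| KP deficit | Power at true 12: raw | Power: back-transformed | One-sided error at 15: raw | Error: back-transformed |
|---|---|---|---|---|
| 12 | 0.903 | 0.521 | 0.0233 | 0.0000 |
| 15 | 0.904 | 0.581 | 0.0244 | 0.0001 |
| 20 | 0.901 | 0.696 | 0.0225 | 0.0004 |
| 25 | 0.902 | 0.758 | 0.0237 | 0.0023 |

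Over all 16 combinations, raw-scale power is 90-98% with error 2.1-2.7%. Back-transformed power is 21-97% with error 0.0-2.5%. With KP SD 12 and KJD SD 15, back-transformed power is 94-97%, so nothing is lost there.

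**6. The literal reading.** If 15 were left unconverted, the whole 0-100 range would span only 10 units on √(100 − WOMAC), and a difference of 15 could not occur. An analyst is unlikely to act on this, but the text does not exclude it.

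**The case against.** The strongest reply is that the decision scale is already given: the estimate is described as a difference in mean WOMAC total score, so transformation is only a modelling step and a return to points is implied. A valid return exists. Adding each arm's own root-scale variance to its squared mean root recovers exactly 15.00 points in all 16 scenarios. On this view the loss of power belongs to one naive back-transformation, and the choice of method is ordinary SAP content. The low power figures also depend on assumed SDs. The 21% floor needs the arm nearer the ceiling to be the more variable, whereas the reverse is more natural on a bounded scale and shows no loss. The simulation omits covariates, random effects and repeated measures. The error is conservative, and transforming first and falling back second is a coherent sequence.

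Much of this stands as a limit on size: the effect is conditional, illustrative and not a source of false non-inferiority. It is also fair that the sentence on non-inferiority limits in section 10.2 directly follows the relative-risk text, so its use for continuous outcomes is inferred from the objective in section 2.

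The core point survives. The arm-specific correction is not stated anywhere in the protocol. Nor is this merely detail left to the SAP: the protocol itself directs the transformation and fixes the raw margin. A SAP that kept the decision on an untransformed model would depart from the protocol's wording.

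**Conclusion.** The concern holds and should be fixed. Section 10.1 prescribes a change of scale without reconciling it with a margin of 15 raw points, and it gives two overlapping responses to failed model assumptions without an order.

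The consequence is conditional on residuals being judged non-normal. Its size cannot be fixed for this trial, because neither the transformation nor the KP mean is given. Under the assumptions above, with SD 15 in both arms, simple back-transformation overstates a true 15-point loss by 0.8 to 1.7 points and cuts power from 90% to 52-76%. Under other assumed SDs the loss is larger or absent. The direction is against showing non-inferiority.

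The transformation is not needed for validity at this sample size: in the skewed scenarios examined, the raw-scale comparison kept its error near 2.5% and its power at 90% or more.

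**What to change.** In section 10.1:

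1. State that the primary non-inferiority decision is always made on the untransformed 24-month difference in mean WOMAC total score (KJD minus KP), with the lower 95% limit compared with −15, in both the mixed model and the fallback regression.
2. If residuals are non-normal, keep the raw-scale model with robust or bootstrap intervals, and report transformed models as sensitivity analyses only.
3. State that non-normal residuals alone do not trigger the switch to 24-month regression.

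In section 10.2, apply the same rule to every continuous secondary outcome that is compared with a non-inferiority limit.

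A transformed model with a prespecified transformation and a prespecified method returning a raw-scale mean difference and interval would also be coherent, but it is more complicated and not needed here.

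The cost is two or three sentences in 10.1 and one in 10.2. The sample size does not change: 527 per arm keeps 90% power on the raw scale.

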**Nature and extent of the burden and risks associated with participation, benefit and group relatedness:** The benefit of a KP over KJD might be the swifter and slightly better clinical effect of treatment although at the expense of the original joint and with the higher risk of revision surgery later in life. The benefit of the KJD over a KP is that the original joint is preserved with the chance of postponing placement of a KP and decreasing the chance of revision surgery later in life, although with the burden of a 6-week distraction period with the chance of skin pin-tract infections, and possibly a slightly (non-clinically relevant) lesser clinical benefit.

In both arms, at 7 moments questionnaires must be filled out without the need of a clinic visit. At baseline for both treatments, and in case of KJD treatment additionally at 24 months a clinic visit takes place (the latter for a study specific x-ray) in addition to the typically 4 clinic visits performed in regular practice. In both arms a comparable number of knee radiographs is made in regular care and for KJD the 24 months study specific x-ray will be made.

In both arms the chance of failure is <5% in the first year after treatment. Failure can be due to multiple reasons, mostly persisting pain, leading to either revision surgery in case of a KP or placement of a first KP in case of KJD. Additionally, there is a chance of infection in both arms. In case of KJD these are primarily superficial skin pin tract infections, in generally successfully treatable with oral antibiotics. In both arms a small chance for deeper infections up to osteomyelitis are seen, needing i.v. antibiotics and/or nettoyage or even removal of the frame in case of KJD or early revision surgery in case of KP. Rehabilitation after the intervention(period) is similar for both treatment arms.

Patients randomised to knee distraction in the GODIVA trial are asked to participate in this GODIVA-bone add-on study. In case of consent, the burden will be a knee-MRI, knee-CT, and DEXA scan at pre-treatment and 2 years post-treatment, which will take two times an 60-120 min extra out-patient visit time. These image techniques are considered minimally

[figure not shown]
invasive with CT and DEXA with radiation exposure. Additionally, a vena puncture for 2 times 7 cc blood samples (serum and plasma) at both timepoints provides a minimal risk. The urine samples are considered riskless. There is no direct benefit for the patient.

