## 1. INTRODUCTION AND RATIONALE

Knee osteoarthritis (OA) is a degenerative joint disease characterized by articular cartilage degeneration, periarticular bone changes, and soft tissue impairment causing pain, stiffness, and functional limitations, and considerable loss of quality of life (1,2). In the Netherlands, yearly almost 30,000 (total and unicompartmental) knee prostheses (KP) are placed for patients not sufficiently responding to conservative therapy or joint preserving surgery ('end-stage knee OA') (3).

About 30% of KP's are implanted under the age of 65. These patients have a significantly higher risk of revision surgery later in life, i.e., up to 35% and 20% in men and women, respectively in the age category 50-55 (4). When a first prosthesis is implanted after the age of 65, the need for revision surgery significantly decreases (see figure 1).

[figure not shown]
*Lancet 2017; 389: 1424-30*

*Figure 1 Lifetime revision rate of knee replacement*

Revision surgery is complex, costly, and accompanied by multiple complications (5-7). With the increasing life expectancy, focus on patient empowerment, and the wish to stay active and independent up to high age, this problem is anticipated to further increase. Treatments that can postpone a KP are therefore desired.

Knee-Joint-Distracton (KJD) is such a treatment and uniquely demonstrates cartilage tissue repair (8,9) as well as amelioration of complaints. KJD places the two bony ends of the knee joint at a distance of about 5 mm for a period of about 6 weeks according to prescribed procedures as described and advised by the NOV (the Dutch orthopaedic society), see appendix S.

[figure not shown]
Several prospective studies and two RCTs have been performed. All KJD treated patients reached a ‘patient acceptable symptom state’ based on KOOS/WOMAC questionnaire domains and > 85% reached response according to modified OMERACT-OARSI criteria (own analysis) (8) see also table/figure above.

The mechanism behind its effect is still largely unknown but thought to be related to the absence of mechanical stress on the joint combined with intra-articular biochemical changes which allow damaged cartilage to repair itself (10).

Based on the data from previous research and preliminary combined analyses, bone parameters are considered key in response to knee distraction treatment. (Spil W et al., Ann Rheum Dis 2013;72,) (Black A, J Orthop 2022;32,) (Curry Z et al. Menopause 2022;29,);

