### **11.4 Benefits and risks assessment, group relatedness**

The benefits and risks for the patients treated with KP are fully according to clinical practice. Patients should realize that in the Netherlands KJD is still not reimbursed and is only provided within the setting of the current clinical trial.

The benefit of a KP over KJD might be the swifter and slightly better clinical effect of treatment although at the expense of the original joint and with the higher risk of revision surgery later in life. The benefit of the KJD over a KP is that the original joint is preserved with the chance of postponing placement of a KP and decreasing the chance of revision surgery later in life, although with the burden of a 6-week distraction period with the chance of skin pin-tract infections, and possibly a slightly (non-clinically relevant) lesser clinical benefit.

In both arms, at 7 moments questionnaires must be filled out without the need of a clinic visit. At baseline for both treatments, and in case of KJD treatment additionally at 24 months a clinic visit takes place (the latter for a study specific x-ray) in addition to the typically 4 clinic visits performed in regular practice. In both arms a comparable number of knee radiographs is made in regular care and for KJD the 24 months study specific x-ray will be made.

In both arms the chance of failure is <5% in the first year after treatment. Failure can be due to multiple reasons, mostly persisting pain, leading to either revision surgery in case of a KP or placement of a first KP in case of KJD. Additionally, there is a chance of infection in both arms. In case of KJD these are primarily superficial skin pin tract infections, in generally successfully treatable with oral antibiotics. In both arms a small chance for deeper infections up to osteomyelitis are seen, needing i.v. antibiotics and/or nettoyage or even removal of the frame in case of KJD or early revision surgery in case of KP. Rehabilitation after the intervention(period) is similar for both treatment arms.

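### Section 10.1 rests non-inferiority on the per-protocol set, with a completion condition in the KJD arm only, and gives a conflicting ITT result no consequence

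*Protocol*

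**What the plan says.** Section 10.1 of the protocol compares the lower 95% confidence limit for the 24-month WOMAC difference with a margin of 15. On the analysis set it states: "The above analysis will be performed primarily on the per protocol (PP) population", which it defines as "patients that received their randomised treatment (and completed the 6 week distraction period for patients randomised to KJD only". On the other set it states: "The analysis will be repeated, for sensitivity reasons, for the ITT population defined as all patients who were randomized to one of the treatments". It does not say what follows if one set meets the margin and the other does not.

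Earlier in the same section the protocol says that both sets have biases, that neither is a gold standard for non-inferiority, and that "these approaches can make critical differences to the results of a trial".

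Three other places bear on the point:

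- Section 1 describes the intervention: "KJD places the two bony ends of the knee joint at a distance of about 5 mm for a period of about 6 weeks".
- The Summary and section 11.4 describe infection risk. Section 11.4 says "In both arms a small chance for deeper infections up to osteomyelitis are seen", and the Summary gives the consequences as "needing i.v. antibiotics and/or nettoyage or even removal of the frame in case of KJD or early revision surgery in case of KP".
- Section 8.6 expects no withdrawal from treatment, excludes from PP anyone not treated as randomised, and says of crossover: "Note that this can be only one way, refusing KP will not result in KJD".

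**The concern.** Two features combine. First, one analysis set carries the verdict although the protocol itself warns that the choice of set can change the result. ITT will be reported, so a conflict would be visible, but section 10.1 attaches no consequence to it.

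Second, the completion condition works after randomisation and in one arm only. Deep infection can lead to frame removal in one arm and early revision in the other, and the protocol presents these as counterparts. If the frame comes off before the distraction period is complete, the KJD patient drops out of the deciding comparison. The KP patient did receive the randomised treatment and stays in. Such an exclusion may be related to outcome.

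There is little room to absorb a shift: the assumed true deficit is 12 and the margin is 15.

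**Working it through.** **Inputs.** From section 4.4: margin 15, assumed true difference 12 in favour of KP, SD 15, one-sided 2.5%, 90% power, 527 per arm. The share of KJD patients who do not complete distraction and their outcome gap are not in the protocol; the values used below are assumptions.

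**Reproducing the plan's figure.** Normal approximation: n = 2 × 15² × (1.960 + 1.282)² / (15 − 12)², which rounds up to 526. The t-test calculation gives 527 with power 0.9004. The stated 527 is confirmed.

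**Precision.** SE = 15 × √(2/527) = 0.924. Power at a true difference of 12 = Φ(3/0.924 − 1.96) = 0.901.

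**Shift from the exclusion.** Let f be the share of KJD patients excluded from PP and g the number of points by which they score below completers. The PP estimate then exceeds the all-randomised estimate by b = f × g in favour of KJD. If the all-randomised deficit is exactly 15, the chance that PP declares non-inferiority is Φ(b/0.924 − 1.96). The small loss of precision from the exclusions is ignored.

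| f (assumed) | g (assumed) | b | False non-inferiority |
|---|---|---|---|
| none | none | 0 | 2.5% |
| 1% (about 5 of 527) | 10 | 0.1 | 3.2% |
| 2% (about 11 of 527) | 10 | 0.2 | 4.1% |
| 1% | 20 | 0.2 | 4.1% |
| 2% | 20 | 0.4 | 6.3% |

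**Tipping point.** The error reaches 5% when b = 0.924 × (1.960 − 1.645) = 0.29 points, for example 2% × about 15 points or 1% × 29 points.

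**Opposite direction.** Suppose the excluded patients convert to KP and score 10 points higher. PP then penalises KJD. At an all-randomised difference of 12, PP power is Φ((3 − b)/0.924 − 1.96): 0.881 for b = 0.1 and 0.858 for b = 0.2. Simulation with the reduced PP numbers gives 0.880 and 0.855.

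**Requiring both sets.** Simulation with 527 per arm, known SD, and 1% / 2% of KJD patients outside PP:

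- Excluded patients 10 or 20 points lower, all-randomised deficit 15: both sets pass in 2.5-2.6% of runs, against 3.2-6.4% for PP alone.
- No outcome difference, true difference 12: both pass in 89.5% / 89.3%.
- Excluded patients 10 points higher, all-randomised difference 12: both pass in 88.0% / 85.5%, practically the same as PP alone.
- Excluded patients 10 points lower, PP difference 12: ITT becomes the limiting set, with power 0.881 / 0.858 by the formula above. Both-pass power is about the same.

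**The case against.** The strongest case for the plan is that PP as the primary set is deliberate and defensible. Crossover can only run towards KP, and KJD patients who receive a KP pull the ITT arms together, which is anti-conservative for non-inferiority. This stands. It is a reason to keep PP as one of the deciding sets and not to replace it with ITT.

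A six-week treatment and a single operation cannot have identical definitions of treatment received. This also stands, and a reader who took the KJD-only condition to be an error in itself would go too far. Failures after completed treatment (a first KP after KJD, revision after KP) stay in PP in both arms, so the unequal handling is confined to distraction that ends early.

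A reader might infer that PP favours KJD, or that the bias is large. The documents support neither. They speak of a small chance of deep infection, give no rate of early frame removal, and leave the direction open. Non-completion of 5% or 10% would produce much larger errors, but nothing in the protocol supports such rates. The inflation also presupposes that the all-randomised difference is the target, which the protocol did not choose for its primary analysis.

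A reader might also infer that a contrary ITT result would be ignored. The protocol does not say so. It is silent, and the SAP, which is not at hand, may address it. But section 10.1 already fixes the deciding set and the subordinate role of ITT, so as written a failed ITT analysis would leave the verdict unchanged.

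**Conclusion.** The point holds as a weakness in the decision rule, worth correcting before outcomes are known. Section 10.1 lets one set decide after saying that neither set can be relied on alone, and that set contains a one-arm, post-randomisation exclusion that may be linked to outcome.

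The size is unknown. Under the illustrative assumptions of 1-2% excluded and a 10-point gap, the effect is modest in either direction: false non-inferiority of 3.2-4.1% instead of 2.5%, or a loss of about 2 to 5 percentage points of power. Doubling the error to 5% needs share × gap of 0.29 points. These figures rest on SD 15, 527 analysed per arm and the all-randomised difference as target. They do not show that the trial's conclusion will be wrong.

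**What to change.** In section 10.1, and correspondingly in the SAP, state that KJD is declared non-inferior only if the lower 95% limit of KJD minus KP lies above -15 in both the PP set, as now defined, and the ITT set. PP continues to protect against crossover towards KP diluting the difference; ITT protects against selective exclusion.

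An analysis with PP defined in both arms as allocated procedure performed may be added as a non-deciding sensitivity analysis. It should not replace the deciding PP set: it would nearly coincide with ITT and would bring patients who convert early to KP into both deciding sets.

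The cost is wording only, since both analyses are already planned; no patients or data are added. Power at a true difference of 12 falls from about 90% to about 89-89.5% if patients outside PP do not differ in outcome. It falls to about 86-88% if 1-2% are outside PP and differ by 10 points in either direction, with 12 being the difference in the set that is not shifted.
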